9.0 STUDY PLAN DESCRIPTION

9.1 Pre-study focus group discussions

We will hold about 3 pre-study focus group discussions. During these FDGs, participants will propose the timing and frequency of the messages during pre-study focused group discussions (FGDs). Perceptions of PWE on use of mobile phone text messages to improve adherence will also be evaluated during the three pre-study FGDs before the roll out of the study. These will involve about 10 PWE and one of their family members in each group. The aim of these FGDs will be to inform the preferred timing and frequency of the messages to be sent out during the study. We will also review the nature of the messages and how best to relay sensitive information, especially for shared phones. Finally, we will establish the content of public health promotional messages (not related to epilepsy adherence) such as use of bednets and the types of messages controls would want to receive. These discussions will be recorded. The audio records will be stored in cabinets under lock and key and destroyed upon transcription. Paper transcriptions will be stored under lock and key until all have been electronically replicated and validated.

9.2 Roll out of the SMS trial

9.2.1 Identification of Participants

Participants will be identified from the epilepsy clinic in Kilifi and three clinics in Nairobi (two APHRC clinics in Korogocho and Viwandani, respectively and one KAWE-led clinic). These PWE will have utilized the clinics more than once and live within either the KHDSS for participants in Kilifi or the NUHDSS for participants in Nairobi. The epilepsy clinic in Kilifi has a database (built under an approved protocol: KEMRI/SERU/CGMR-C/125/3701) that has over 3,500 patients to date, who have accumulated from 30 patient visits a day, 10 of whom are usually new. They will be approached by the study clinician during their routine clinic visit. In Nairobi, participants will be identified from an on-going survey which is part of the EPInA studies. This survey is being conducted by APHRC to identify people with a likely diagnosis of epilepsy living in informal settlements in Korogocho and Viwandani. The diagnosis is confirmed by trained clinicians at two APHRC clinics conveniently located within the study areas. The identified PWE will be added to an epilepsy database from which participants for this study will be identified. Additional PWE will be identified from one KAWE-led clinic in Nairobi.

In Kilifi, record logs usually taken during routine care will be reviewed from the database of those attending the epilepsy clinic and then those at Kilifi County Hospital. In Nairobi, records from participants identified during an on-going epilepsy survey in two slum dwellings conducted by APRHC and records from patients attending KAWE-led clinics will be screened for eligibility.

9.2.2 Eligibility criteria

9.2.2.1 Inclusion criteria

- (i) Children or adults with a diagnosis of epilepsy ascertained by a clinician at the epilepsy clinic
- (ii) Taking anti-seizure medications at the time of the study
- (iii) Living within an area defined as the Kilifi Health Demographic Surveillance System, or the Nairobi Urban Health and Demographic Surveillance System at the time of the study or attending the epilepsy clinic in Kilifi or a KAWE-led clinic in Nairobi
- (iv) Able to give written informed consent or assent in addition to parental consent (if aged between 13 and 17 years old) to participate in the study either by themselves or in the presence of an independent witness

(v) Access to a basic mobile phone in the household

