1.4 PROTOCOL SYNOPSIS

Full Title	Evaluation of a Mobile Messaging Service (Text and / or Graphic) in Improving Adherence with Ensured Supply of Anti-seizure Medications in People with Epilepsy in Kilifi and Nairobi, Kenya
Short Title	SMS Trial
Trial Phase	Not Applicable
Objectives	
Primary Objective: To examine the impact of sending text or graphic SMS reminders on anti-seizure medication (ASM) adherence people with epilepsy in Kilifi and Nairobi, Kenya
 
Secondary Objectives: To describe the perceptions and perspectives of people with epilepsy (PWE) and their caregivers on the use of text and graphic SMS reminders to improve adherence to anti-seizure medications (ASMs) among PWE in Kilifi and Nairobi, Kenya
 
To compare the effectiveness of text versus graphic messaging service in improving adherence in people with epilepsy in Kilifi and Nairobi, Kenya
 
To identify the factors associated with improvement in adherence, improved quality of life (QoL) and reduction in stigma-associated suffering among PWE and family members.
 
To document the common adverse drug reactions (ADRs) related to commonly prescribed ASMs and the plasma levels associated with these ADRs among PWE in Kilifi and Nairobi, Kenya
 
To evaluate the cost-effectiveness of the interventions in each of the sites

Trial Design	Partially-blinded randomized controlled trial
Sample Size	1200 participants (900 participants in the intervention arm (300 receiving text SMS, 300 receiving graphic SMS, 300 receiving both text and graphic) and 300 in the control arm/receiving non-reminder messages) in each site
Study Population	We will include participants who fulfil the following criteria:

	
 i. children or adults with a diagnosis of epilepsy ascertained by a clinician at the epilepsy clinic, taking anti-seizure medications at the time of the study, ii. persons living within an area defined as the Kilifi Health Demographic Surveillance System (KHDSS) or the Nairobi Urban Health Demographic Surveillance System (NUHDSS) at the time of the study, or attending the epilepsy clinics in Kilifi or the Kenya Association for the Welfare of persons with Epilepsy (KAWE) clinics in Nairobi iii. persons able to give written informed consent or assent (for children 13-17 years old) iv. persons with access to a basic mobile phone in the household either through direct ownership, a caregiver or a member of the household nominated by the PWE

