In LMICs, several studies have considered the effectiveness of text messaging (SMS) interventions to improve health workers' practices (Kallander et al, 2013; Zurovac et al, 2011), as a learning tool, and to improve adherence to medications and care, particularly antiretroviral drugs (de Tolly et al., 2012). To inform policy makers about the feasibility of facility-based SMS messaging interventions, coverage data on mobile phone ownership and SMS use among health workers and patients are needed. More studies are also needed to ascertain the usefulness and potential negative consequences of mobile phone messaging, both SMS and graphic / picture messaging (multimedia messaging service (MMS)), over extended periods of use for self-managing chronic conditions (de Tolly et al., 2012). It has been estimated that over two-thirds of the population in Africa is covered by a mobile network with a penetration rate of 93%, reaching just under a billion mobile phone subscribers across the continent <https://data.gsmaintelligence.com/api-web/v2/research-file-download?id=18809326&file=the-mobile-economy-sub-saharan-africa-2015-infographic-1482139932154.pdf> . In 2009, in collaboration with the Kenyan National Bureau of Statistics, the Financial Sector Deepening Kenya survey asked questions about mobile phone usage, ownership, and monthly expenditure on airtime, as well as detailed demographic questions concerning income, education level and housing type (32,748 individuals located at 646 communities: <http://www.fsdkenya.org>). Based on three cluster surveys, 85% of the population reported using a mobile phone. In rural areas, mean phone ownership was 39% (90% range: 14%–43%) compared to urban regions where it was 58% (90% range: 65%–80%). Ownership was determined by education level rather than gender in urban areas, whereas in the rural areas and among poor urban communities, 20% owned their own phone, while most households shared a mobile phone, and usage was higher among men. InfoDev's findings from a survey of 6 districts in Kenya found no notable gender difference in mobile phone activities, but this did not translate into an absence of a gender disparity in mobile phone ownership (<http://www.infodev.org/articles/mobile-usage-base-pyramid-kenya>). Both phone owners and phone sharers reported similar monthly expenditure on mobile phones and, surprisingly, both groups spent approximately the same proportion of their income on airtime (13% and 10%, respectively) (Wesolowski et al., 2012). Another finding from both surveys was the deliberate sacrificing of food or bus fare to pay for airtime, in the belief that a call may lead to work. In addition, an audit of mobile phone ownership and usage assessment conducted at the epilepsy clinic in Kilifi in 2013 showed that, of the 222 PWE interviewed,

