
19% (44/222) owned a mobile phone, and 85% (189/222) could access mobile phones through close caregivers living with them. In Nairobi, the phone ownership rates are likely to be even much higher, considering this is an urban area and the capital city of the Country but PWE may be disadvantaged due to their medical condition leading to other psychosocial consequences such as lack of employment and poor marriage prospects.

This rapid assimilation of mobile phone technology within Africa makes it culturally compelling to help reduce the treatment gap of one of the most common neurological conditions worldwide (Panter-Brick et al., 2006). To our knowledge, no studies have used mobile phone messaging to improve adherence to ASMs and address stigma. The application of text messaging for behavioural change for mental and neurological disorders is at an early stage of research. Randomised controlled trials of such use of text (SMS) or picture (MMS) messaging, and / or with an auditory component are scarce, with few from semi-literate low-resource settings. There are few reported trials on antiretroviral treatment adherence from Kenya (van der Kop et al., 2018) and from India (De Costa et al., 2010). There is also a paucity of studies that assess community-based adherence interventions alongside improved supply of ASMs to health care centres in rural areas to bridge the adherence treatment gap.

5.2 Name and description of the investigational product(s),

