8.0 DESCRIPTION OF THE INTERVENTION

8.1 Intervention

The intervention will be a short message service (SMS) reminder sent to the mobile phones of participants in the intervention group reminding them to take their anti-seizure medications. This will be a behavioural intervention with no investigational medicinal product. Each SMS (text or graphic or both) adherence message will be 120–140 characters long. To increase the probability that that the PWE or family member will read the messages and support family members with epilepsy, message will be randomly complemented with a quote (up to 60 characters long) and unrelated to epilepsy treatment, but designed to be motivating, entertaining, or merely attention-getting. This motivational element was used with success in the health workers adherence to antimalarial guideline studies. The graphics will be hand drawn by a local illustrator and the accompanying text of no more than 15 characters will be scanned and sent as low-resolution jpeg files, suitable for the MMS format that is compatible with basic phones.

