9.2.5. Randomisation

Participants will be randomized to four groups, with randomisation assigned via a computer-generated sequence by an independent statistician. The database manager will not know details of those SMS are being dispensed to. An allocation ratio of 1:1:1:1 across the 4 arms

will be used. A random sampling technique using computer-generated sequences will be used to ensure epilepsy factors such as focal features, age and gender are balanced between the intervention groups or arms. The SMS randomisation platform will be linked to a central database that stores a pre-generated randomization sequence, which will be generated once at the beginning of the study. Each participant will be randomized once, failure to which the system will alert the data manager and decline the request. The data manager will use an automated system to send out the messages and they will be blinded to participant details. In addition, to prevent cross-contamination due to exchange of information among participants, we will emphasise the need to keep allocation among confidential the participants and schedule follow up visits for participants in different arms on different days. However, cross-contamination may still occur in the community, and this will be considered during interpretation of the findings.

Figure 1. Recruitment strategy and randomization

*All people with epilepsy in the databases will be screened for eligibility

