12.0 STATISTICS

12.1 Determination of sample size

The minimum sample size determination will be based on reducing the adherence treatment gap from the current estimates of 62% in Kilifi ((Ibinda et al., 2017a) aiming for a proportion of improvement of 40%-50%. Previous studies have shown non-adherence of >60% even among clinic attendants, especially when symptoms subside. Assuming a refusal/non-consent/attrition rate of 10% and design effect of 1.5 (assuming possibility of modest clustering), if we recruit 300 patients at each arm, i.e., total of 1200 patients, we will have 95% power to detect a 50% improvement in adherence. Therefore 1,200 PWE will be randomized into 4 arms as follows: text SMS (N=300), graphic SMS (N=300), both text and graphic SMS (N=300) and control/non-reminder SMS (N=300). An allocation ratio of 1:1:1:1 across the 4 arms will be used. Since no prevalence estimates exist for the Nairobi site, we will utilise a similar sample size for each site. This sample size determination will account for these unprecedented withdrawals by recruiting a surplus of participants, assuming a proportion of 20% loss to follow up.

Table 2. Sample size adjusted for 10% attrition at varying improvements and powers

Improvement	Power			
	80%	90%	95%	
40%	588	786	971	
45%	268	358	442	
50%	154	205	253	

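### No rule covers two participants who share a phone or household, so individual randomisation could send different arms' messages to one handset; the likely dilution is small and cheap to prevent

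*Combined protocol and SAP*

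**What the plan says.** Section 9.2.2.1 asks for "Access to a basic mobile phone in the household". The synopsis (1.4) spells out that access may be "either through direct ownership, a caregiver or a member of the household nominated by the PWE". Section 5.1 shows that sharing is expected. In the Kilifi clinic audit "19% (44/222) owned a mobile phone, and 85% (189/222) could access mobile phones through close caregivers living with them", and survey data for rural and poor urban communities found that "most households shared a mobile phone". Section 8.1 hopes that "the PWE or family member will read the messages and support family members with epilepsy". Section 9.1 puts shared phones on the focus-group agenda, as a matter of relaying sensitive information.

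Section 9.2.5 allocates individuals from one pre-generated sequence in the ratio 1:1:1:1, aiming for balance on focal features, age and gender. It states that "Each participant will be randomized once". Against contamination it offers confidential allocation and different visit days for different arms, and it accepts that some community contamination may remain. Section 12.1 includes a design effect of 1.5 for unspecified clustering. No cluster appears in 9.2.5, 12.2.1 or 12.2.2. No section limits enrolment to one person per phone or household, puts co-residents in the same arm, or checks for duplicate numbers.

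**The concern.** The intervention is delivered to a handset, but the unit of allocation is a person. If two enrolled people with epilepsy are reached through the same phone, the system may send that phone two arms' messages. A control can then see reminders, and a text-only participant can see graphics and in effect receive the combined arm. Section 16.4 keeps identifying information out of the messages, so nothing in a message need show which of the two it is for.

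The safeguards in 9.2.5 address conversation between participants. They do not work when the trial itself sends both message streams to one phone. The design effect does not help either: it allows for extra variance and does not restore a reduced difference between arms. At stake is a bias towards no difference in the main comparison and in text versus graphic.

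**Working it through.** **1. The plan's own figure.** Section 12.1 claims 95% power with 300 per arm for a 50% improvement, with 10% attrition and a design effect of 1.5. Control adherence is 1 − 0.62 = 0.38, and a relative 50% improvement gives 0.57. The effective size is 300 / (1.5 × 1.1) = 181.8 per arm. Two-sided alpha of 0.05 is assumed, since none is stated. With pooled variance and no continuity correction:

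- null standard error: √(2 × 0.475 × 0.525 / 181.8) = 0.0524
- alternative standard error: √((0.38 × 0.62 + 0.57 × 0.43) / 181.8) = 0.0514
- power = Φ((0.19 − 1.96 × 0.0524) / 0.0514) = 95.5%

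The stated 95% reproduces.

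**2. How a pair splits.** For two participants allocated independently 1:1:1:1:

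- same arm: 4 × (1/4)² = 25%
- control with a reminder arm: 2 × 1/4 × 3/4 = 37.5%
- two different reminder arms: 3/4 × 2/4 = 37.5%

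Seen from one control, the partner is in a reminder arm with probability 3/4.

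**3. How many pairs.** The documents give no count, so this is a range under assumptions. Populations are from 7.2 (about 65,000 in the Nairobi surveillance area and 280,000 in Kilifi), with 1,200 participants per site. All participants are treated as area residents. Household size h is assumed. The share of participants with a co-participant at home, by chance alone, is f = 1 − (1 − 1,200/N)^(h−1). If every such pair also shares a phone and an exposed control gains the full reminder effect, exposed controls number 300 × 0.75 × f and the difference shrinks by 19 × 0.75 × f points.

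| Site | h (assumed) | f | Participants | Exposed controls of 300 | Loss from 19 points | Power |
|---|---|---|---|---|---|---|
| Nairobi | 3 | 3.7% | 44 | 8 | 0.5 | 94.5% |
| Nairobi | 5 | 7.2% | 86 | 16 | 1.0 | 93.3% |
| Kilifi | 4 | 1.3% | 15 | 3 | 0.2 | 95.2% |
| Kilifi | 7 | 2.5% | 31 | 6 | 0.4 | 94.8% |

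**4. If epilepsy clusters in households.** Chance co-residence then understates f. In Kilifi, 1,200 of about 3,500 clinic patients are to be enrolled. If an enrolled person's co-resident is also in that database, the second is enrolled with probability of about 1,200/3,500 = 34%. For larger assumed f, on the same worst case:

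- f = 10%: 17.6 points, power 92.2%
- f = 20%: power 87.2%
- f = 30%: power 80.4%

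**5. Cost of allocating by household.** With pairs, the design effect is about 1 + f × ICC. At f = 10% and an assumed ICC of 0.5 it is 1 + 0.1 × 0.5 = 1.05. The 1.5 already allowed is exceeded only if f × ICC > 0.5.

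The text-versus-graphic loss cannot be sized in the same way, because the plan states no target difference for that contrast.

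**The case against.** The strongest reply is that the documents never show two enrolled people on one phone. The passages on sharing describe a patient and a caregiver or household. The formula counts people who live together, who may use different handsets. Household sizes are assumed, and 9.2.2.1 also admits clinic attenders from outside the surveillance areas. The phone figures date from 2009 and 2013, and 5.2 reports rising ownership. The plan also has points where duplicates could surface: the phone audit in 15.0, the pre-message calls in 8.5 and 9.2.3, and the checks on numbers and handsets in 5.2.

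All of this stands as to size. A reader might infer that the arms are contaminated as a matter of fact, and the documents do not support that. A reader might also infer that three pairs in four expose a control to reminders. Three in four is the chance that two participants differ in arm, and only half of those pairs include a control. What the reply does not supply is a rule: none of these checks says what to do when two participants give the same number.

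A second objection concerns the remedy. Participants know their arm (7.1). If someone joined later and took a relative's arm, that arm would be known before consent, which breaks concealment. This is correct, and it determines how the fix must be written.

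**Conclusion.** The gap is real and minor. Individual allocation with shared phones permitted, and no same-phone or same-household rule, leaves open a route of contamination that the trial itself creates and could avoid. By chance co-residence it would affect about 4% to 7% of participants in Nairobi and 1% to 3% in Kilifi. The loss is about 1 point or less of the 19-point difference, and roughly 0.3 to 2 points of power from 95.5%.

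These figures rest on assumed household sizes, all participants living in the surveillance areas, every co-resident pair sharing a phone, and exposed controls gaining the full effect. Those last three assumptions push the figures up; clustering of epilepsy in households would push them beyond this range. The documents do not support calling this a threat to the trial's main conclusion. The case for acting is that prevention is cheap.

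**What to change.** - **9.2.5, unit of allocation.** Make the registered phone number or household the unit. Ask each candidate about eligible co-residents and others using the same phone, register all of them before any is randomised, and give them one shared allocation. Do not add a member to the randomised sample after the household has been allocated, because that person's arm would be predictable.
- **Alternative.** Enrol only one randomly chosen participant per phone or household. This avoids both the shared allocation and the household clustering.
- **Platform.** It already declines a repeat randomisation of the same person. Extend that check to duplicate phone numbers and households.
- **12.2.2.** If households are allocated, use standard errors clustered on household.

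The cost is one platform rule, one question at screening and one line in the analysis plan. Arms may depart slightly from 300 and the balancing factors may be slightly less even. Household linkage must also be collected for clinic attenders living outside the surveillance areas. The added design effect, about 1.05 at 10% paired and an ICC of 0.5, sits within the 1.5 already budgeted.

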9.2.2.2 Exclusion criteria

Participants who meet all the inclusion criteria above will not be eligible for inclusion in the study if they:

- i. have intellectual disability
- ii. do not have access to basic mobile phones
- iii. are currently enrolled in ongoing interventions aimed at improving their health care

9.2.3 Consenting/Assenting and screening for eligibility

Consenting and/or assenting (for children aged 13 to 17 years old) will be done by field workers during initial contact and participants booked for the first study visit. Investigators will emphasize that participation in the study is voluntary. All participants will have the study explained to them including potential risks and obligations before giving written informed consent and/or assent. Once consented and/or assented, participants will be screened for eligibility based on the above-mentioned set of inclusion and exclusion criteria. Screening will be conducted by study fieldworkers in collaboration with the study clinicians.

Participants who meet the inclusion criteria at the screening visit will be telephoned by a fieldworker a week prior to sending out the SMS to assess availability of mobile phone access. They will also be asked about any new medical complaints and concomitant medication since their screening visit.

